1.0 PROTOCOL TITLE

1.1 Effect of Group Led Creative Writing on Mood in Cancer patients.

1.2 Brief Title: Effect of Creative Writing on Mood in Cancer Patients.

2.0 STUDY SPONSORSHIP

2.1 Funding Sponsor: Penn State Hershey Cancer Institute
Fifty Shades of Pink (Breast Cancer Endowment Fund)

2.2 Primary Sponsor: Penn State Hershey Cancer Institute

3.0 PROTOCOL ABSTRACT

The primary purpose of this study is to determine whether creative writing in newly diagnosed cancer patients and those with recent progression in their disease will have a positive impact on their mental health. Using a randomized controlled trial approach, emotion thermometers will be employed to evaluate participants' responses on a number of domains, such as anxiety, depression, despair, and anger along with a series of survey questions to monitor changes in depressive and anxiety symptoms. Open-ended survey questions will be used to capture how a creative writing intervention impacts participants' experience of their illness. [name]'s *Write from the Heart* program focuses more on creative writing rather than cancer focused topics. Patients in the intervention arm will complete – one and a half hour group sessions every two weeks over the span of 3 months. Participants in the active control arm will be provided a book (i.e., *Writing Down Bones* by Natalie Goldberg) about creative writing and will be asked to do activities for 1.5 hrs every 2 weeks for a period of 2-3 months.

4.0 OBJECTIVES

4.1 Primary Objectives:

- Mental wellness before and after intervention in the intervention and control groups. A validated Emotional Thermometer Scales will be used to predict changes in parameters reflecting participants' mental health pre- and post-intervention. Survey questions focused on symptoms of depression and anxiety will be used to monitor for changes in mental wellness pre- and post-intervention.

4.2 Secondary Objectives:

- Comparison of mood scores, depression and anxiety symptoms versus frequency of attendance in the intervention arm.
- Comparison of somatic symptom burden between intervention and control group.
- Difference in mood scores, depression symptoms, anxiety symptoms, and somatic symptoms after workshop between genders.
- Difference in mood scores, depression symptoms, anxiety symptoms, and somatic symptoms between patients living alone versus with family.
- Difference in mood scores, depression symptoms, anxiety symptoms, and somatic symptoms between various cancer types.
- Difference in mood scores, depression symptoms, anxiety symptoms, and somatic symptoms in individuals who have previously attended a creative writing class versus those who have not.
- Difference in mood scores, depression symptoms, anxiety symptoms, and somatic symptoms in individuals who completed control group activity and then enrolled in the workshops and attended at least one session.
- Comparison of the frequency of emergency room visits and hospitalizations between intervention and control group during the study period.

Institutional Review Board

- Comparison of cancer status (stable, progressing, in remission) between intervention and control group.

5.0 BACKGROUND

5.1 Scientific Background and Gaps

Cancer is a life-threatening, feared diagnosis and is a source of great distress in patients. Hence in addition to treating cancer, one must address the emotional well-being of patients.

Creative activity has a significant history in providing a wide range of psychological and physiological benefits for cancer survivors (King et al., 2012). When individuals experience a stressful life event or crisis, the higher verbal functions in the cerebral cortex become less accessible (Hass-Cohen, 2008.) Therefore, patients who face such stressful life events of cancer are often left without words to describe their experiences of feelings (Green & Young, 2015). Findings from Green and Young (2015) suggest that creative visual expression, engaging both in an individual and the therapeutic setting, offered an opportunity for young adult survivors to express their emotions from deep within their bodies. It created self-understanding and a sense of healing.

In another study by Bolton (2007) patients indicated that they found the therapeutic writing process beneficial. For example, one participant narrated, "It made it less traumatic than it might have been otherwise." Creative writing has been recognized to explore and express personal thoughts, feelings, and experiences. Lau Tsu (1973) showed that writing facilitated patients' ability to discover what they thought felt and remembered. Therapeutic creative writing enhanced their awareness of and ability to express issues to which attention and focus are required. (Esterhing BA et al., 1999)

There is a substantial area of agreement that language, narrative storytelling, forms an essential element in the construction of a coherent identity, sense of self and connectedness to others, and therefore, it is a powerful tool in creative therapy (Smyth, 1998; Wright & Chung, 2001). Roe and Davidson (2005) argue that processes of re-authoring one's life story are actually integral components of the recovery process itself. A study by Stanton (2002) of breast cancer patients prompted to write about their cancer experience showed a significant decrease in self-reported somatic symptoms and medical appointment visits for cancer-related morbidities three months after participation in the study. A follow-up study by Stanton (2013) encouraged breast cancer patients to create personal websites to chronicle their experience and to communicate with their social network. This study showed significant improvement in positive mood and depressive symptoms after 6 months, particularly in patients undergoing medical therapy at that time. These studies further support that the act of narrative story telling can improve patient wellbeing.

Furthermore, King et al. (2012) suggest that writing can contribute to repair of symbolic functioning and contribute to the development of personal identity. The researchers concluded that, of all the creative arts, writing is least dependent on equipment and/or special environments. Writing workshops are probably better provided by professional writers than by mental health professionals. When health professionals provide activities such as a writing workshop, there is a risk that identification with the illness is reinforced. On the other hand, when a professional writer provides a similar activity, it is the participant's identity as a writer that is reinforced, rather than their identity as a person with an illness. (King et al., 2012)

Moreover, there is emerging consensus in the UK and USA that there might be advantages if writing therapy is received from facilitators who themselves are trained writers and can work in collaboration with health care professionals. (Hunt & Sampson, 1998; Mc Loughlin, 2004).

5.2 Previous Data

We conducted a pilot study to determine feasibility whether cancer patients can be enrolled, randomized and retained for four weeks for creative writing classes (Feasibility was defined as 50% of our enrolled patients on intervention arm (IA) could attend at least 2 classes). We anticipated enrolling 45 patients over the period of 2 months with randomization into 2 arms: IA and standard of care (SOC). "Write from the Heart" a series of creative writing workshops (CWW) were conducted on IA. Subjects in IA had four, 2-hour weekly CWW whereas SOC arm did not receive any session. We used validated Emotional Thermometer Scales (ETS), ranging 0 (best)-10 (worst), to predict changes in a number of parameters reflecting patient's mental health pre and post intervention. ETS has five dimensions (distress, anxiety, depression, anger and need help), which are all continuous variables. Due to time constraints we were not able to accrue the desired number of patients. A total of 16 patients were accrued in 1 month period -11 in IA and 5 in SOC. 7 out of 11 (63%) patients enrolled in IA attended at least 75% of classes. Comparisons were made using two-sample T-tests. Although sample size was small, IA did show a decreasing pattern on Total Emotion Score (TES), particularly in depression and anxiety scores (See table 1 and figure 1, 2). For each visit, post-class scores were lower than pre-class scores. We observed that it is feasible for cancer patients to attend focused workshops geared towards mental health wellbeing. IA showed a trend towards mood improvement, although was not shown to be statistically significant which may be attributed to the small sample size. Having shown the feasibility of such a study, we hope to increase the sample size and include more specific methods for quantifying mood improvement in the patient groups. In addition, after reviewing the suggestions (post completion of the study) from the patients who attended these sessions on the study, we concluded that 1.5hours of class twice a month is feasible and helpful for patients.

Variable	Categories	SOC	IA
Baseline TES	Mean (SD)	5.8 (4.3)	6.5 (6.2)
Baseline TES	Median (Range)	5 (0-10)	5 (0-20)
Final TES	Mean (SD)	5.7 (5.1)	0.3 (0.5)
Final TES	Median (Range)	7 (0-10)	0 (0-1)

Table 1: Mean and Median TES at baseline and after intervention in SOC versus IA.

[figure not shown]

Fig 1: Total Emotions Scores before and after each visit.

[figure not shown]

Fig 2, A-D: Emotions Scores before and after each visit; A-D: A-Distress, B-Depression, C-Anxiety, D- Anger

6.0 RATIONALE AND HYPOTHESIS

6.1 RATIONALE:

Cancer generates an increased sense of distress than non-malignant diseases with poor prognoses (Mishel et al., 1984). Persistent mental distress for prolonged periods leads to anxiety and depression. The rate of depression in cancer patients is thought to be up to three times higher than in the general population (Linden et al., 2012). Depression leads to a poorer quality of life (QOL) and affects patient outcomes, with depression resulting in higher rates of mortality in cancer (Colleoni et al., 2000, Pinquart et al., 2010). A meta-analysis revealed that minor or major depression increases mortality rates by up to 39%, and that patients displaying even few depressive symptoms may be at a 25% increased risk of mortality (Satin et al., 2009). The impact of mood and mental wellbeing on cancer progression is considered important by doctors and patients, with >70% of oncologists and 85% of patients believing that mood affects the progression of cancer (Lemon et al., 2004). Our previous data as mentioned before shows that creative writing is feasible and needs to be further studied to understand the effect of group therapy with focused workshop in newly diagnosed or patients with recent recurrence. In addition, we observed that the emotional thermometer scale was not enough to capture the mood of the patients. For example, some patients felt significantly better after attending these sessions and were able to cope with their symptoms but the emotional scale did not reflect that benefit.

6.2 HYPOTHESIS:

This study aims to look at the impact of participating in creative writing workshop group *Write from the Heart*, on cancer patients' emotional well-being. Keeping previous studies in mind, a

Institutional Review Board

professional writer will conduct the workshops, which will enhance the participant's ability to express and enhance their awareness. We anticipate that participation in the workshop will result in a positive effect on the parameters being studied, enabling patients to cope with their illness/cancer better. We hypothesize that group sessions of creative writing workshop could be better than individual sessions.

7.0 CHARACTERISTICS OF THE STUDY POPULATION

7.1 Target Population

Adults with a new diagnosis of cancer, at any stage OR progression of cancer- within three months of enrollment.

7.2 Accrual

We aim to accrue 60 eligible patients over a time span of 4months at the Milton S. Hershey Medical Center.

7.3 Key Inclusion Criteria

- Adult >20 years of age
- Any patient with a cancer diagnosis.
- Ability to understand English language and ability to write without any functional difficulty
- ECOG performance status 0-3

7.4 Key Exclusion Criteria

- Inability to give informed consent
- Severe psychiatry illness (e.g., uncontrolled depression, schizophrenia or psychosis)
- Severe cognitive impairment
- Pregnant females
- Inability to write or understand English

7.5 Vulnerable Populations

None

7.6 Populations vulnerable to undue influence or coercion

If a patient who works for or has some affiliation to Pennsylvania State University happens to be in the potential participant pool, we will verbally stress to him/her that their participation is voluntary and will not influence her care or any outcomes related to Penn State.

7.7 Subject Recruitment

We will recruit participants from our outpatient cancer clinics at HMC (Hershey Medical Center). We will create a pamphlet describing our study briefly and study staff contacts, then distribute in all cancer clinics. This will be given to every cancer patient at any stage, with recurrence, or with progression at HMC. We will also send emails to physicians and nurses at outpatient cancer clinics at HMC for study description and our contact details. If patients are interested, we (study staff) will conduct initial eligibility screening and obtain informed consent from patients to initiate study follows up.

8.0 CONSENT PROCESS AND DOCUMENTATION

8.1 Consent Process

8.1.1 Obtaining Informed Consent

Physician-Investigators of the study will identify patients from their clinic and patients will be approached to participate in the study. Study staff will then discuss the study in detail to make the patient aware of the workshops, intervention, and time commitment involved with the study. If the patient is interested, study staff will answer any remaining questions and obtain written informed consent at the patient's clinic visit with their primary oncologist.

8.1.2 Coercion or Undue Influence during Consent

If a patient affiliated with Pennsylvania State University happens to be in the potential participant pool, we will inform them that their participation is voluntary and will not influence her care or any outcomes related to Penn State.

8.1.3 Waiver of Authorization

Not applicable

8.2 Consent Documentation**8.2.1 Written Documentation of Consent**

Study staff members will assist with data and consent collection. If the patients are unable or not competent to give consent, they will not be enrolled in the study.

8.3 Consent – Other Considerations**8.3.1.1 Non-English Speaking Subjects**

Not included.

8.3.1.2 Cognitively Impaired Adults

Not included.

8.3.1.3 Subjects who are not yet adults (i.e., infants, children, teenagers)

Inclusion criteria: greater than 20 years of age

9.0 STUDY DESIGN**9.1 Phase**

Phase II

9.2 Design

The focus of this study is to determine the difference in mental health parameters following the participation of cancer patients in a creative writing workshop. Participants will be randomized within strata formed by cancer type in order to assure that these potentially important confounding variables are balanced across groups. Patients will be enrolled on a rolling basis over a four to five-month period, allowing patients in intervention arm to participate in 2-3 months workshops (workshops would be held once every 2 weeks). Patients in control arm will be provided a book (*Writing Down Bones* by Natalie Goldberg) about creative writing and will be asked to do activities for 1.5 hours every 2 weeks. After three months, control group participants can join creative writing workshops at their discretion for the remaining period for writing workshops. Both group members will receive follow up surveys twice a month for two months at the completion of the participant's two-month study period.

9.3 Study Duration

Estimated time to enroll all subjects = 3-5 months (Patients will start being enrolled after IRB approval and we will continue the enrollment up to 4-5 months from the time the 1st class starts for the intervention group)

Length of a participant's participation = 2 - 6 months; Follow up after participant's completion of classes = 2 months

9.4 Endpoints:**9.4.1 Primary endpoints:**

- Mood scores before (at baseline) and after intervention (after completion of entire sessions - this may vary as some patients may not be able to complete six sessions). A validated Emotional Thermometer Scales will be used to predict changes in parameters pre and post-intervention.
- Severity of depression and anxiety symptoms before and after intervention between two groups. Validated Depression and Anxiety questionnaires will be used to predict changes, the PHQ-9 and GAD-7 respectively.

9.4.2 Secondary endpoints:

[figure not shown]
- Mood and symptoms before and after at least 2 sessions of intervention.
- Self-reported somatic symptoms pre and post intervention in two groups. We will use the Somatic Symptom Scale – 8 (SSM-8) to quantify somatic symptom burden.
- Difference in scores and symptoms between various genders.
- Difference in scores and symptoms between patients living alone versus with family.
- Difference in scores and symptoms in different cancer types.
- Difference in scores and symptoms versus number of classes attended.
- Differences between individual mood scores for patients in the control group who later switch to intervention group and attend at least one session
- Mood and symptom scores up to 2 months after completion of the study.

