10.0 STUDY PROCEDURES

10.1 Methods: After enrollment as above, co-investigators of this study or the assigned coordinator will be doing the consent. Patient will be randomized to intervention and control arms in a 2:1 ratio. The intervention arm will receive a dedicated workshop for one and a half hours every 2 weeks. We aim to start a 6 month long program with weekly creative writings workshops, and patient enrollment in the study will continue through the 1st 4.5 months of the 6 month period so that the last enrolled patient could complete 2 classes per month for two months. Each patient will be asked to attend at least two classes per month for a total of two months. These workshops will be held at Hershey Medical Center (HMC). At the initiation of the study along with consent we will collect baseline scores in both groups for each parameter as below. Somatic Symptom Burden (SSM-8 - Figure 2 - reference section), depression symptoms using PHQ-9 (Figure 3 – reference section), and anxiety symptoms using GAD-7 (Figure 4 – reference section) will be collected monthly and following intervention completion.

We will collect mood scores pre and post each session. We will use Emotional Thermometer Scale (EMS) from [name] (Feb. 2010), diagram for scales is shown in figure 1. Please see supplementary index for a letter of permission to use from [name]. We will give the Thermometer scales and collect scores pre and post each session and also collect scores pre and post completion of entire course. Control group will do EMS on monthly basis along with other parameters. At the end of the study we will review all participants' medical charts to count view the number of emergency room visits and hospitalizations each participant experienced during the study period. These will be further broken down in categories based on cancer

Institutional Review Board

related vs non-cancer related visits. We will also review their most current cancer disease status after completion of the workshops and categorize whether their status is considered to be stable, progressing, or in remission. Both groups will also receive follow up mood and symptom surveys twice a month for up to 2 months after completion of the participant's two to three month study period.

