The control arm will receive a book (i.e., *Writing Down Bones* by Natalie Goldberg) on creative writing and asked to read and do writing activities for one and a half hours once every two weeks. At the completion of the two-month participation or completion of 4 sessions control patients will be given the opportunity to enroll in the creative writing workshops for the remainder of the study period of 6 months. We will collect scores from control arm through the same Emotion Thermometers Scale on a monthly basis. Pre-intervention scores will be obtained at the time of consent or one week prior to the planned start of session 1 for workshop (either in the clinic if possible or mail the score sheet to patients with an enclosed stamped envelope for return of the scales). Depending on participant preference, we can send them emails of the REDCAP surveys containing the same information at set intervals. A sample of the REDCAP surveys is included in supplementary materials. We will also send participants in the control arm a stamped return envelope on a monthly basis if not able to get score sheets in a clinic or over REDCAP, depending on patient convenience and preference. We will call the participants once every 3-4 weeks to check in on their progress. Please see a calendar at the end for details.

To assess for possible confounding results of patients participating in the concurrent exercise study, we will ask participants if they are also enrolled in the exercise study at enrollment and perform a subset analysis for patients who are in the exercise study. They will be randomized into either control or intervention group in the same manner as the other patients in the study. We will additionally include a section of the survey to ask about regular exercise (more than 30 minutes, three times a week) and do a subset analysis of these patients as well.

We will be collaborating with the Department of psychiatry at HMC - [name], [name], and [name]. Any subject who requests psychiatry follow up will be referred to [name]. If participants report the presence of suicidal ideation per question nine on the PHQ-9 [i.e., Thoughts that you would be better off dead or of hurting yourself in some way], they will be referred on an urgent basis to [name] or [name]. In the event [name] and/or [name] are unavailable for follow-up, If any active suicidal thoughts are reported, participants will be referred directly to Emergency Department at Hershey Medical Center.

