10.6 Control group activities: Participants randomized into the control group were asked to maintain their usual follow up while also reading a book on creative writing for one and a half hours every other week for three months, logging their activity for verification of task completion. Their mode scores will be measured as mentioned above.

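### The primary 'after' mood score is timed by each patient's own attendance in the workshop arm and by the calendar in controls, and no common time point or contrast is named

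*Combined protocol and SAP*

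**What the plan says.** Section numbers are those of the first protocol text in the file.

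- **Primary mood endpoint (9.4.1).** Baseline is compared with a score taken "after completion of entire sessions - this may vary as some patients may not be able to complete six sessions". No week or month is given.
- **Other primary endpoint (9.4.1).** "Severity of depression and anxiety symptoms before and after intervention between two groups", by PHQ-9 and GAD-7, again without a time point. Section 10.1 collects both monthly and once more when the intervention ends, without limiting this to one arm.
- **Thermometer collection (10.1).** For sessions, the plan is to "collect scores pre and post each session and also collect scores pre and post completion of entire course". For controls: "Control group will do EMS on monthly basis along with other parameters".
- **Requested attendance (10.1).** "Each patient will be asked to attend at least two classes per month for a total of two months", that is, four classes, where 9.4.1 still speaks of six. Section 9.3 gives "Length of a participant's participation = 2 - 6 months".
- **End of the control period.** Section 10.1: "At the completion of the two-month participation or completion of 4 sessions control patients will be given the opportunity to enroll". Section 10.6 has controls "reading a book on creative writing for one and a half hours every other week for three months". Section 9.2 lets controls join after three months, and 11.1 at the end of week 12.
- **Analysis (11.1, 11.2).** A repeated-measures linear mixed model is planned, with no primary time point or contrast. Power of at least 80% is stated for 0.45 SD with 40 and 20 patients, four unidentified time points and a within-patient autocorrelation of 0.2.

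**The concern.** A randomised comparison needs the outcome read on the same clock in both arms. Here the workshop clock stops when the patient stops attending, and the control clock stops at a calendar point that the protocol gives in several ways. Two things follow.

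First, any change in mood with time that is unrelated to the workshop enters the between-arm difference whenever the arms are read at different times. Second, the timing of the score is itself a consequence of attendance, which is likely to be related to how well the patient is.

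There is also a difference in setting. A workshop patient's last thermometer may be filled in straight after a class, and 5.2 reports that pilot scores were lower after class than before at every visit. Controls have no equivalent moment. Any of these could create or hide a difference in the primary endpoint.

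**Working it through.** **1. The two clocks side by side.**

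| | Workshop arm | Control arm |
|---|---|---|
| Thermometer | before and after each class; before and after the course | monthly |
| 'After' point | end of own sessions, allowed to vary | not defined |
| End of period | four classes over two months (10.1); six sessions (9.4.1) | two months or four sessions (10.1); three months (9.2, 10.6); week 12 (11.1) |
| PHQ-9, GAD-7 | monthly and at completion | monthly and at completion |

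For the thermometer, the arms share no defined 'after' time. For PHQ-9 and GAD-7 a shared monthly schedule exists; what is missing is a statement of which assessment is primary.

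**2. The plan's own power figure.** Inputs from 11.2: n = 40 and 20, difference 0.45 SD, four time points, autocorrelation 0.2. Alpha of 0.05 is from 11.1; two-sided is assumed, since the plan does not say. With first-order autoregressive correlation, the variance of a mean of four scores, in SD² units, is

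v = [4 + 2(3×0.2 + 2×0.2² + 0.2³)] / 16 = 5.376 / 16 = 0.336.

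SE = √[0.336 × (1/40 + 1/20)] = √0.0252 = 0.159. Power = Φ(0.45/0.159 − 1.96) = 80.9% by the normal approximation (79.6% with the noncentral t). The stated 80% is reproduced, for an average over four time points common to both arms.

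**3. Power for one 'after' score.** With v = 1, SE = √0.075 = 0.274 and power = Φ(0.45/0.274 − 1.96) = 37.6%. Adjusting for baseline, with an assumed baseline-to-final correlation of 0.2, 0.5 or 0.7, gives 38.9%, 47.5% or 63.3%. So the before/after comparison described in 9.4.1 is not the one that 11.2 powers.

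**4. Illustration of the timing effect.** Assume no workshop effect, the same drift in both arms, arms read one month apart (two versus three months), and a single unadjusted after-score comparison. False difference b = drift × 1 month. Type I error = 1 − Φ(1.96 − b/0.274) + Φ(−1.96 − b/0.274).

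- Drift 0.1 SD per month: b = 0.1 SD, type I error 6.5%.
- Drift 0.2 SD per month: b = 0.2 SD, type I error 11.3%.

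The drift rates are assumptions; the documents give none.

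**5. Common assessments available before controls join.** If controls may join at two months, baseline, month 1 and month 2 give three assessments. A fourth, month 3, falls before joining only under the three-month or week-12 text.

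**The case against.** The planned analysis is not a single self-timed score. It is a mixed model over repeated measures, which can handle visits at different times. That is true in principle, but only if time since randomisation is modelled and a contrast is named, and 11.1 does neither. The study schema is not shown, and the calendar mentioned in 10.1 is not in the readable text, so a visit schedule may exist there. It would help, but 9.4.1 itself says that the timing varies.

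Several stronger readings are tempting, and the documents do not support them.

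- *The workshop score could fall anywhere from week 4 to month 6.* Week 4 needs a patient to attend every weekly class, although 10.1 gives the arm a class every two weeks. Six months is the outer length of participation, not a stated time for the score. The documented mismatch is mainly two versus three months.
- *The false difference could reach 0.4 SD.* That takes a two-month gap together with the higher assumed drift. The only control data, the pilot SOC means in 5.2, are flat: 5.8 then 5.7, a change of 0.1/4.3 ≈ 0.02 SD. They come from five patients at most, so they do not exclude drift either.
- *About 36% of workshop patients would have no final score.* In the pilot, 4 of 11 attended under 75% of classes. That is attendance, not missing scores, and 9.4.1 can be read as scoring patients who fall short of six sessions. The pilot SOC summary suggests some final scores were lost, but that arm had no classes, so anchoring to completion cannot be the cause.
- *PHQ-9 and GAD-7 have the same fault.* They have a monthly schedule and lack only a named time point.

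**Conclusion.** The point holds, most firmly for the Emotion Thermometer. Section 9.4.1 states a rule that makes the primary assessment time depend on attendance after randomisation. The control arm follows another rule, with an end point given inconsistently, and the analysis section supplies nothing that would restore comparability. For PHQ-9 and GAD-7 the gap is narrower: the primary assessment is not identified.

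How large the bias is, and in which direction, cannot be derived from the documents. The 0.1-0.2 SD false difference and 6.5-11% type I error rest on an assumed drift, a one-month mismatch and a single unadjusted after-score comparison. They show that a modest mismatch can matter against a 0.45 SD target; they are not estimates for this trial.

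A reader might infer that one month-2 score would solve the problem at no cost. It would solve the timing, but with power of about 38% unadjusted at 0.45 SD.

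**What to change.** In 9.4.1 and 11.1:

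1. Define the primary assessments for all three scales at common fixed times from randomisation in both arms: baseline and the monthly assessments already scheduled, with a short window.
2. Collect them from every randomised patient whatever their attendance, by the REDCap or mail route in 10.1, and not immediately after a class. Section 10.1 describes the monthly envelope for controls only, so the workshop arm must be added.
3. Use only assessments made before a control joins a workshop for the primary between-arm contrast. Four sessions at two-week spacing starting at week 0 end at week 6, so some controls could join before a month-2 score; state how such scores are handled.
4. Name the contrast and the time scale within the planned mixed model, and restate the power for that contrast.
5. Keep the score after completion as a secondary, workshop-arm measure.
6. Reconcile the passages on six versus four sessions and on the two-month, three-month and week-12 control periods.

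The cost is mostly wording, plus thermometer surveys sent to workshop patients outside class. Some patients will be measured before their last class. The restated power may be less favourable, because about 81% applies only to an average over four common time points.
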